5 ANALYSIS SETS

In accordance with International Conference on Harmonization (ICH) recommendations in guidelines E3 and E9, the following analysis sets will be used for the analyses.

Detailed criteria for analysis sets will be laid out in Classification Specifications (CS) and the allocation of subjects to analysis sets will be determined prior to database hard lock.

5.1 Intent-to-Treat Population

The Intent-to-Treat (ITT) population is defined as all subjects who were randomized in this study. The ITT population will be analyzed by treatment arm as randomized (i.e., treatment arm based on randomization assignment). The ITT population will be used to conduct efficacy analyses, unless otherwise specified. For the ORR, only ITT subjects with measurable disease at baseline will be included in the analysis.

5.2 Safety Population

The safety (SAF) population is defined as all randomized subjects who received at least 1 dose of study drug. The safety population will be used to conduct safety analyses by treatment arm as treated (i.e., based on the actual study drug the subject mostly received, rather than the study drug to which the subject was randomized). The safety population will be used to conduct safety analyses.

6 ANALYSIS VARIABLES

6.1 Efficacy Endpoints

6.1.1 Primary Efficacy Endpoint(s)

6.1.1.1 Primary analysis

The primary endpoint is time to PSA progression (TTTP), where PSA progression is defined as a $\geq 25\%$ increase and an absolute increase of $\geq 2 \mu\text{g/L}$ (2 ng/mL) above the nadir (i.e., lowest PSA value observed post baseline or at baseline), which is confirmed by a second consecutive value at least 3 weeks later.

There are 2 planned analyses, one final analysis at the total planned 75 PSA progression events and one interim analysis at 80% of the total planned events (about 60 PSA progression events). TTTP will be formally tested at both interim analysis and final analysis at 2-sided 0.0244 and 0.0429 significance level, respectively, for efficacy according to the O'Brien-Fleming boundary as implemented by Lan-DeMets alpha spending function [Lan-DeMets, 1983]. Data cut-off dates will be set when the planned number of events is reached for the interim and final analyses. If the exact number of events at interim and final analyses are different than planned, the significance level will be adjusted accordingly, based on the O'Brien-Fleming method with

a Lan-DeMets alpha spending function. The family-wise type I error rate for this study is strongly controlled at 5% (2-sided) that allows the study to declare positive on primary endpoint TPP on the ITT population.

Only results from central lab PSA samples taken before the initiation of any new antineoplastic prostate cancer therapy after the start of study drug will be considered and are referred to in this section.

The date of PSA progression is the first date the PSA progression is observed. In patients with PSA progression, TPP will be calculated as the time from randomization to the date of first observation of PSA progression.

In patients with no PSA progression, TPP will be censored on the date of the last PSA sample taken. Patients entering the open-label phase without PSA progression would be censored on the last PSA prior to first open-label treatment.

In patients with no baseline PSA and patients with no post-baseline PSA results, TPP will be censored on the date of randomization.

6.1.1.2 Sensitivity analyses of primary endpoint

Appendix 1 - Summary of Sensitivity Analyses of Primary Endpoint summarizes the different TPP definitions used in sensitivity analyses of the primary endpoint.

Sensitivity analysis 1 - TPP_1 - Assess the Impact of Treatment Discontinuation

The impact of treatment discontinuation will be assessed in two sensitivity analyses.

In the first sensitivity analysis, subjects with study treatment discontinuation prior to PSA progression will be censored at the date of last PSA assessment before treatment discontinuation without evidence of PSA progression. The primary analysis of TPP will be repeated after accounting for this change in censoring rules. The hazard ratio and 95% CIs will be reported.

In the second sensitivity analysis, subjects who discontinued study treatment without evidence of PSA progression or on-study death will be considered as having a TPP event at the date of last dose of study drug. The primary analysis of TPP will be repeated after accounting for these new events. The hazard ratio and 95% CIs will be reported.

Sensitivity analysis 2 - TPP_2 - Assess the Impact of Subsequent Anti-neoplastic Therapy

In this sensitivity analysis, subjects' PSA samples taken after the initiation of any new antineoplastic prostate cancer therapy after the start of study drug will also be considered, which means subjects who start new anti-neoplastic treatment prior to PSA progression will not be censored at the date of last PSA assessment before initiation of subsequent anti-neoplastic therapy without evidence of PSA progression. The primary analysis of TPP will be repeated after accounting for this change in censoring rules. The hazard ratio and 95% CIs will be reported.

Sensitivity analysis 3 – TPP_3 - rPD (INV), SSE, New therapy, and Death as event impact

TPP_3 events are defined as the PSA progression, rPD (Investigator), SSE, New antineoplastic therapy, and Death (within 24w after EOT).

In patients with a TPP_3 event, TPP_3 is calculated as the time interval from the date of randomization to the first date of the PSA progression, rPD (Investigator) or SSE, New antineoplastic therapy, death, whichever occurs first.

In patients with no TPP_3 event, TPP_3 will be censored on the date of PSA assessment prior to the data analysis cut-off date. In those patients, patients with no baseline PSA assessment, patients with no post baseline radiographic assessments, TPP_3 will be censored on the date of randomization.

Sensitivity analysis 4 - TPP_4 - Assess the Impact of PSA results from local laboratory tests.

In this sensitivity analysis, subjects' PSA results, which are collected from local laboratory assessment instead of central, will be taken as central records, and the primary analysis of TPP will be repeated after accounting for this change in PSA assessments. The hazard ratio and 95% CIs will be reported.

6.1.2 Secondary Efficacy Endpoints

For variables derived, unless otherwise specified, only results taken before the data analysis cut-off date will be considered and are referred to in this section.

6.1.2.1 rPFS

Radiographic progression-free survival (rPFS), where rPFS event is defined as the time from randomization to the first objective evidence of radiographic disease progression assessed by Investigators or death (defined as death from any cause within 24 weeks from study drug discontinuation), whichever occurs first.

Radiographic disease progression is defined by Response Evaluation Criteria in Solid Tumors (RECIST) version 1.1 for soft tissue disease or the appearance of 2 or more new lesions on bone scan. The documentation and confirmation required for the determination of radiographic progression is listed in the following table.

Table 3 Protocol-specified Documentation for Radiographic Evidence of Disease Progression

Date Progression Detected (Visit) [†]	Criteria for Progression	Criteria for Confirmation of Progression (Requirement and Timing)	Criteria for Documentation of Disease Progression on Confirmatory Scan
Week 13	Bone lesions: ≥ 2 new lesions compared to baseline bone scan	Timing: ≥ 6 weeks after progression identified or at week 25 visit	≥ 2 new bone lesions on bone scan compared to week 13 scan (≥ 4 new lesions compared to baseline bone scan)

	Soft tissue lesions: progressive disease on CT or MRI by RECIST v1.1	No confirmatory scan required for soft tissue disease progression	Not applicable
Week 25 or Later	Bone lesions: ≥ 2 new lesions on bone scan compared to best response on treatment	No confirmatory scan required	Not applicable
	Soft tissue lesions: progressive disease on CT or MRI by RECIST v1.1	No confirmatory scan required for soft tissue disease progression	Not applicable

CT: computed tomography; MRI: magnetic resonance imaging; RECIST v1.1: Response Evaluation Criteria in Solid Tumors version 1.1.

† Progression detected by bone scan at an unscheduled visit prior to week 25 will require the same criteria for documentation of disease progression as week 13 with a confirmatory scan at least 6 weeks later or at the next scheduled scan.

In patients with no rPFS event, rPFS will be censored on the date of last radiographic assessment prior to the data analysis cut-off date. In those patients, patients with no baseline radiographic assessment, patients with no post baseline radiographic assessments and patients with all post-baseline radiographic assessments documented as “Not Evaluable”, the radiographic progression free survival will be censored on the date of randomization. Patients entering the open-label phase without rPFS event would be censored on the date of last radiographic assessment prior to first open-label treatment.

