## 12.8 Soft Tissue Assessment (RECIST)

**Table 1 – Time point response: patients with target (+/- non-target) disease.**

Target lesions	Non-target lesions	New lesions	Overall response
CR	CR	No	CR
CR	Non-CR/non-PD	No	PR
CR	Not evaluated	No	PR
PR	Non-PD or not all evaluated	No	PR
SD	Non-PD or not all evaluated	No	SD
Not all evaluated	Non-PD	No	NE
PD	Any	Yes or No	PD
Any	PD	Yes or No	PD
Any	Any	Yes	PD

CR = complete response, PR = partial response, SD = stable disease, PD = progressive disease, and NE = inevaluable.

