Not applicable	Not applicable	No	Not applicable \$
Not applicable	Not evaluated or Not Done	No	NE
Not evaluated or Scan not Done	Not PD	No	NE

* The category “Any” includes all possible categories (incl. NE or NA or Not Done). The category “Not PD” includes: CR, Non-CR/Non-PD, NA, NE and Not Done.

^ Missing assessments during study visits will not be imputed. Missing assessments for “Uequivocal new lesions” will be reported as “Missing” and will lead to “NE” for the derived RECIST Overall Response.

\$ The RECIST overall time point response will only be derived to “Not applicable” for patients with no target and no non-target soft tissue lesions at study entry in absence of new unequivocal lesion.

Definition of Best RECIST Overall Response

In patients with measurable soft tissue lesions at study entry (all patients, who have at least one target lesion), the best RECIST overall response in the soft tissue disease is the best of the RECIST overall time point response assessment reported at any time during or at the end of the treatment period, up to the start of any other antineoplastic prostate cancer therapy. The best RECIST overall response assessment is according to the following decreasing order, starting with the possible best response: CR, PR, SD, Non-CR/Non-PD, PD, NA, NE. For patients still on treatment after or by the cut-off date, the best RECIST overall response can be derived as the best of the RECIST overall time point response assessments recorded for the time on study up to the data cut-off date. Patients with no post-baseline assessment at any visit are reported in the ‘Not evaluated’ category.

The best RECIST overall response will be derived from the assessments provided by the investigators.

Definition of Best Overall Response

At each time point, the overall time point response assessment reported by the investigators are based on the combination of the time point assessments on soft tissue on target lesions, non-

target lesions and apparition of new lesions (i.e. RECIST), and the time point response assessment on bone scan.

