The best overall response is the best of the overall time point response assessment reported at any time during or at the end of the treatment period, up to the start of any other prostate cancer therapy. The best of the overall time point response assessments is according to the following decreasing order, starting with the possible best response: CR, PR, SD, Non-CR/Non-PD, unconfirmed PD, PD, NA (for Investigator only), NE. For patients still on treatment after or by the cut-off date, the best overall response can be derived as the best of the overall time point response assessments recorded for the time on study up to the data cut-off date. Patients with no post-baseline assessment at any visit are reported in the 'Not evaluated' category.

The best overall response will be derived from the overall time point response assessments provided by the investigators.

Table 5 describes the possible combinations of tumor response to report the overall timepoint response assessment.

Table 5 RECIST Combined Time Point Response Provided for any Combinations of Tumor Responses in Soft tissue Lesions and Bone Lesions

RECIST 1.1	Bone Scan	The Combined (i.e., Overall) Time Point Response	
CR	CR	CR	
CR	NA	CR	
NA	CR	CR	
CR	NON-CR/NON-PD	PR	
CR	PDu	PR	
PR	CR	Not NE = & not PD	PR
PR	NON-CR/NON-PD		PR
PR	PDu		PR
PR	NA		PR
SD	CR	Not NE = & not PD	SD
SD	NON-CR/NON-PD		SD
SD	PDu		SD
SD	NA		SD
PD	Any	PD	
Any	PD	PD	
NON-CR/NON-PD	CR	Not NE = & not PD	NON-CR/NON-PD
NON-CR/NON-PD	NON-CR/NON-PD		NON-CR/NON-PD
NON-CR/NON-PD	PDu		NON-CR/NON-PD
NON-CR/NON-PD	NA		NON-CR/NON-PD
NA	NON-CR/NON-PD	NON-CR/NON-PD	
NA	PDu	PDu	
Any but PD	NE	NE	
NE	Any but PD	NE	
NA	Not applicable	NA	

PDu: unconfirmed Progression of Disease.

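### rPFS is censored at the last scan whether or not it was evaluable, which slightly overstates Kaplan-Meier rPFS; separately, a blank new-lesion field turns a derived PD into NE

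*SAP*

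**What the plan says.** **Censoring.** SAP 6.1.2.1 gives the general rule for patients without an event: "rPFS will be censored on the date of last radiographic assessment prior to the data analysis cut-off date". Patients who enter the open-label phase without an event "would be censored on the date of last radiographic assessment prior to first open-label treatment". Neither sentence asks whether the scan was evaluable. NE scans appear in one exception only: "patients with all post-baseline radiographic assessments documented as" Not Evaluable are censored at randomisation, as are those with no baseline or no post-baseline scan. Protocol 7.4.2 defines rPFS but gives no censoring rule. All the sensitivity analyses in SAP 6.1.1.2 and Appendix 1 concern time to PSA progression (TTPP).

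**Event.** The rPFS event in SAP 6.1.2.1 is the "first objective evidence of radiographic disease progression assessed by Investigators or death", where death counts within 24 weeks of stopping study drug.

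**Time point response.** SAP 6.1.2.7, Table 5 combines soft tissue and bone scan. One row reads "Any but PD NE NE" (soft tissue, bone scan, combined), and a mirror row covers NE soft tissue with a bone scan that is not PD. PD in either modality gives PD. In Table 4, the footnote says that a missing new-lesion assessment "will be reported as “Missing” and will lead to “NE” for the derived RECIST Overall Response", with no exception. Yet both Table 4 and the RECIST table in Protocol 12.8 carry the row "PD Any Yes or No PD", and a similar row for non-target PD.

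**The concern.** In the wording of SAP 6.1.2.1, an NE scan is still a radiographic assessment, so it can set the censoring date. The all-NE exception accepts that such scans do not support progression-free follow-up. The general rule credits the same scans as follow-up once the patient has a single readable one. At stake are the Kaplan-Meier curve, median and landmark rates for rPFS. The hazard ratio would be affected mainly if NE scans were more common in one arm.

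The footnote is a second, smaller matter. A PD in target or non-target lesions is PD for either value of the new-lesion field, so a blank cannot change the answer. The footnote nevertheless changes it to NE.

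**Working it through.** The documents give no rPFS event count, power or NE rate, so there is no figure of the plan to reproduce. The first check is on the text; the second shows size under assumptions.

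**1. The rule applied to one patient.** Scans fall on day 85 (week 13) and every 84 days thereafter (Protocol 5.3.1.2), so week 49 is day 85 + 3 × 84 = 337.

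| Week 13 | Weeks 25, 37, 49 | Censored under SAP 6.1.2.1 | Last evaluable scan |
|---|---|---|---|
| NE | NE, NE, NE | randomisation | none |
| readable, no progression | NE, NE, NE | day 337 | day 85 |

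In the second row the credit beyond the last evaluable scan is 337 − 85 = 252 days, or 3 × 84.

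**2. Size, first simulation.** Assumptions: 120 and 60 patients, exponential progression times with medians of 40 and 15 months, 84-day scans, 15% dropout per year, cut-off at 27 months, 300 replicates. Each replicate was analysed under both censoring rules.

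- NE at random in 5 to 15% of scans: 5 to 14% of censored patients are credited with extra time. The 18-month rPFS is overstated by 0.2 to 1.1 points, and the HR does not change. At 10% NE the estimates are 0.737 against 0.733 for enzalutamide (0.4 points) and 0.442 against 0.435 for placebo (0.7 points), with HR 0.383 under both rules.
- NE in 5% of scans in one arm and 15% in the other: the HR moves by about 0.007 in either direction.
- NE clustered in the same patients (15%, with 60% persistence): 0.762 against 0.734 (2.8 points) and 0.485 against 0.436 (4.9 points), with HR 0.390 against 0.387. Across the clustered scenarios the overstatement is 2 to 5 points.

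**3. Size, second simulation.** Assumptions: 180 patients randomised 2:1, control median 14.8 months (a control-arm figure from another trial cited in Protocol 1.1, borrowed for illustration), HR 0.5, 15 months of accrual plus 12 of follow-up, 10% dropout per year, 300 replicates.

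| NE rate, enzalutamide / placebo | Patients whose censoring date moves | HR, last scan | HR, last evaluable scan | Control median in months, last / last evaluable |
|---|---|---|---|---|
| 2% / 2% | 2.2 | 0.528 | 0.528 | 15.60 / 15.58 |
| 5% / 5% | 5.6 | 0.527 | 0.527 | 15.85 / 15.78 |
| 10% / 10% | 11.3 | 0.537 | 0.538 | 15.99 / 15.83 |
| 10% / 5% | 9.6 | 0.521 | 0.525 | 15.77 / 15.70 |
| 5% / 10% | 7.2 | 0.539 | 0.535 | 15.72 / 15.62 |

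The two rules should be compared within a row, because each row is a separate set of simulated trials. The average move ranges from about 78 to 94 days. The low end falls below 84 only because replicates with no affected patient were averaged in as zero.

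Both simulations treat an NE scan as carrying no information at all. Where only one modality is unreadable, they overstate the effect.

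**4. The footnote.** Take target PD with the new-lesion field blank. If the true value is Yes, Table 4 gives PD; if No, it gives PD. The footnote gives NE. Keeping PD imputes nothing, so it respects the no-imputation principle in SAP 7.12.1. In the ranking for best RECIST overall response (SAP 6.1.2.7), a patient whose only post-baseline result is such a PD moves from PD to NE. The ORR counts CR or PR among patients with measurable disease at baseline (SAP 7.4.2.7). PD and NE are both non-responses, so neither numerator nor denominator changes.

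**The case against.** The strongest reply is that this hardly matters. rPFS is a secondary endpoint whose p-values are to be read descriptively (SAP 7.1), the PSA-based primary endpoint is untouched, and the HR barely moves. Response by visit is summarised (SAP 7.4.2.7), so the frequency of NE will be visible. All of that stands, and it sets the severity. It does not remove the inconsistency within one paragraph of SAP 6.1.2.1.

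A reader might infer that progression could not have been seen at an NE visit, or that bone disease always goes unassessed there. Table 5 does not support that. A time point is also NE when soft tissue is unreadable and the bone scan was read, and PD in the readable modality still gives PD. The extra time is not fully assessed, rather than unassessed.

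A reader might also infer that a blank new-lesion field deletes rPFS events. The documents do not say so. The footnote governs the derived RECIST response, which serves best RECIST overall response and ORR. The rPFS event rests on investigator-assessed progression, SAP 6.1.2.7 describes a separate overall response reported by the investigators, and nothing routes rPFS through Table 4. What remains is an unnamed variable: Table 4 is itself built from investigator assessments, and SAP 6.1.2.1 never says which response defines progression.

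On the footnote, one can say that the rows list Yes or No and the footnote deals with a third state, missing. That is formally right, but both possible values lead to PD.

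Protocol 12.11 suggests imaging in local hospitals during a crisis. That makes NE scans possible, but the documents give no rate.

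**Conclusion.** The point holds as a low-severity correction to the wording. Under SAP 6.1.2.1, each trailing NE scan adds about 84 days of progression-free time that was not fully assessed. Kaplan-Meier rPFS is slightly overstated: 0.2 to 1.1 points at 18 months with 5 to 15% NE at random, and 2 to 5 points only if NE scans cluster as assumed. The HR moves by about 0.007 or less. All of these sizes rest on assumed NE rates and assumed rPFS distributions.

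The footnote conflicts in effect with the PD rows of Table 4 and affects only the descriptive best RECIST overall response. It would reach rPFS only if progression were programmed from the derived response. In that case, with 5 to 10% of PD scans having a blank field and scanning then stopping, the second simulation loses about 4 to 7 of 69 events. That is a reason to name the source variable, not a finding that events will be lost.

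**What to change.** 1. In both sentences of SAP 6.1.2.1 (general rule and open-label entrants), censor at the last evaluable radiographic assessment, or at randomisation if there is none. Define evaluable, for example as a time point whose combined response in Table 5 is not NE.
2. In the Table 4 footnote, add that a missing new-lesion assessment leads to NE unless target or non-target response is PD, in which case the overall response is PD.
3. State that radiographic progression for rPFS comes from the investigator-reported assessment. The same statement serves time to castration resistance and the TTPP sensitivity analysis that counts progression as an event (TTPP_3), since both use investigator-assessed progression.

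The cost is a few phrases and a line of derivation code; SAP section 1 allows revision before hard lock. Censoring times become slightly shorter and rPFS estimates slightly lower. Under the Table 5 definition, follow-up is also given up at visits where only one modality was unreadable and the other showed no progression. A different definition of evaluable is defensible if it is written down before unblinding.

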6.1.2.2 Time to First Symptomatic Skeletal Event

SSE is defined as radiation to bone, surgery to bone, clinically apparent pathological bone fracture or spinal cord compression.

In patients with SSE, the time to first SSE is defined as the time from randomization to the occurrence of the first SSE prior to the data analysis cut-off date.

In patients with no SSE by the time of the data analysis cut-off date, the time to first SSE will be censored on the last visit date or the date of randomization, or the death date, whichever occurs last. Patients entering the open-label phase without SSE would be censored on the date entering the open-label treatment.

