- ‡ After treatment discontinuation, all subjects MUST undergo long-term follow-up. Long-term follow-up assessments will be composed of post-treatment follow-up and survival follow-up. For those subjects who discontinue study treatment without radiographic disease progression confirmed will undergo post-treatment follow-up (calculated from baseline), include monitoring for survival status, disease progression, new antineoplastic therapies for prostate cancer and symptomatic skeletal events. Subjects will continue to be scanned along with collecting PSA and testosterone every 12 weeks until radiographic progression is confirmed by investigator assessment or the required number of PSA progression events for the final analysis is reached. For those subjects who discontinue study treatment due to confirmed radiographic disease progression will undergo survival follow-up (calculated from date of progression), include monitoring for survival status, new antineoplastic therapies for prostate cancer and symptomatic skeletal events, and the follow-up may be conducted by telephone interview. If seen in clinic, QoL assessment will also be completed until the initiation of new antineoplastic therapy for prostate cancer or the required number of PSA progression events for the final analysis is reached. Additional follow-up contacts may be requested.
- § Or prior to initiation of another investigator agent or new antineoplastic therapy for prostate cancer, whichever occurs first.
- ¶ A brief physical examination is required at each visit, with the exception of the screening visit during which a complete physical examination will be completed.
- †† Laboratory assessments include serum chemistries and hematology.
- ††† For subjects who discontinue study treatment without confirmed radiographic progression, subjects will continue to be collected PSA and testosterone every 12 weeks until radiographic progression is confirmed or the required number of PSA progression events for the final analysis is reached.
- §§ The abdominal-pelvic contrast CT scan or MRI, bone scan, chest x-ray or chest contrast CT must occur within 6 weeks of day 1; otherwise the screening visit assessment must be repeated. Radiographic assessments performed prior to informed consent, as part of the routine care, may be used as the baseline assessment if performed within 6 weeks of day 1 and if digital format images are available for submission to the sponsor.

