6.1.2.5 Time to Initiation of a New Antineoplastic Therapy

The start of a new antineoplastic therapy is based on the information collected in the (new) prostate cancer drug therapy CRF pages about all antineoplastic therapies, including cytotoxic and hormone therapies, initiated for prostate cancer subsequent to the study drug.

In patients with a new antineoplastic therapy initiated for prostate cancer after randomization, time to start of a new antineoplastic therapy is defined as the time interval from randomization to the date of first dose administration of the first antineoplastic therapy.

In patients with no new antineoplastic therapy initiated for prostate cancer after randomization, time to start of new antineoplastic therapy will be censored on the last visit date or the date of randomization, whichever occurs last. Patients entering the open-label phase without initiation of a new antineoplastic therapy would be censored on the date entering the open-label phase.

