- The null hypothesis: TPP for Placebo+ADT and Enzalutamide +ADT are not different
- The alternative hypothesis: TPP for Placebo+ADT and Enzalutamide+ADT are different

The following SAS code will be used to compute the Kaplan-Meier estimates and curves, and the stratified log-rank test:

```
PROC LIFETEST DATA=INPUT  
    ATRISK  
    PLOTS=SURVIVAL(CB)  
    OUTSURV=SURVPL  
    ALPHA=0.05  
    ALPHAQT=0.05 METHOD=KM;  
    TIME AVAL*CNSR(1);  
    STRATA STRATUM1 STRATUM2/ GROUP=TREATMENT;  
    RUN;
```

where INPUT is the input dataset

AVAL is the time to the event variable,

CNSR is 0 (patients with events) or 1 (patients without event, i.e. patient censored)

STRATUM is the stratification variable (volume of disease and prior docetaxel use)

TREATMENT is the treatment variable

Kaplan-Meier methods will be used to estimate the distribution of TPP events by treatment group. The median TPP will be estimated using the corresponding 50th percentile of Kaplan-Meier estimates. A two-sided 95% confidence interval will be provided for this estimate by use of the Brookmeyer and Crowley method. A Kaplan-Meier plot by treatment group will be presented. The estimates of the event free rate on a 3-monthly basis up to 1 year and every 6 months thereafter will be summarized by treatment group, as long as at least 10 patients are at risk.

The benefit of Enzalutamide+ADT compared to placebo+ADT will be summarized by a single HR with its 95% CI based on a Cox regression model stratified for the prior docetaxel use and disease volume. The null and alternative hypotheses regarding TPP can be rephrased in terms of the HR ($\lambda_{\text{ArmA}} / \lambda_{\text{ArmB}}$), where λ_{ArmA} represents the hazard of TPP for Enzalutamide+ADT and λ_{ArmB} represents the hazard of TPP for placebo+ADT. A HR of < 1 indicates that the

TTTP is prolonged for patients randomized to Enzalutamide+ADT compared with patients randomized to placebo+ADT. The null and alternative hypotheses, respectively, can be written as follows:

$$H_0: \frac{\lambda_{ArmA}}{\lambda_{ArmB}} = 1 \quad H_1: \frac{\lambda_{ArmA}}{\lambda_{ArmB}} \neq 1$$

The estimated HR of Enzalutamide+ADT to placebo+ADT, and its 95% confidence interval will be provided.

SAS PROC PHREG will be used for the analysis with the “DISCRETE” option for tie breaker as follows:

```
PROC PHREG DATA = INPUT;  
  MODEL AVAL*CNSR(1) = TREATMENT / TIES=DISCRETE;  
  STRATA STRATUM1 STRATUM2;  
  RUN;
```

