7.4.2.2 Time to First SSE

Time to first SSE will be analyzed using the same analysis methods as for primary analysis of TPP.

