7.4.2.5 Time to Initiation of a New Antineoplastic Therapy

Time to initiation of a new antineoplastic therapy will be analyzed using the same analysis methods as for primary analysis of TPP.

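### Time to first SSE and time to new antineoplastic therapy censor deaths but report Kaplan-Meier rates by arm, so 1-KM overstates cumulative incidence; add a competing-risk estimate

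*SAP*

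**What the plan says.** **Time to first SSE.** SAP 6.1.2.2 defines the event as the first SSE. A patient without one by the cut-off is "censored on the last visit date or the date of randomization, or the death date, whichever occurs last". Protocol 7.4.2 does not count death as an event either.

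**Time to new antineoplastic therapy.** SAP 6.1.2.5 says that, without an event, "time to start of new antineoplastic therapy will be censored on the last visit date or the date of randomization, whichever occurs last". Death is not mentioned.

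**Methods.** SAP 7.4.2.2: "Time to first SSE will be analyzed using the same analysis methods as for primary analysis of TPP". SAP 7.4.2.5: "Time to initiation of a new antineoplastic therapy will be analyzed using the same analysis methods as for primary analysis of TPP". The primary methods in SAP 7.4.1 are a stratified log-rank test, a stratified Cox model, and Kaplan-Meier curves and medians. On rates, that section adds: "event free rate on a 3-monthly basis up to 1 year and every 6 months thereafter will be summarized by treatment group". A time point is shown only "as long as at least 10 patients are at risk".

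**Follow-up.** Under the Protocol Table 1 footnotes, patients who stop treatment for confirmed radiographic progression enter survival follow-up, which is to "include monitoring for survival status, new antineoplastic therapies for prostate cancer and symptomatic skeletal events". The exception is patients who go into the open-label phase. They do not enter that long-term follow-up, and SAP 6.1.2.2 and 6.1.2.5 censor them at open-label entry.

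**What is absent.** For these two endpoints neither document mentions competing risks, cumulative incidence, or a sensitivity analysis that counts death. The fourth TTPP definition that includes death (TTPP_3, SAP 6.1.1.2) belongs to the primary endpoint. SAP 7.1 makes p-values for endpoints other than the primary descriptive.

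**The concern.** A patient who has died can no longer have an SSE or start a new therapy. Kaplan-Meier with death censored treats him as if he kept the same future risk as the survivors. It estimates what would happen if nobody died first. As soon as any deaths precede the event, 1-KM is larger than the real cumulative incidence. Equivalently, the tabulated event-free rate is too low compared with 1 minus cumulative incidence.

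A reader of a table of event-free rates by arm will naturally take the complement as the share of patients affected. If survival or event rates differ between arms, the overstatement differs too, and the absolute difference between arms is then distorted. The two endpoints also handle the same death at different dates (death date versus last visit), with no reason given.

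**Working it through.** **The plan's own figure.** There is none to reproduce: the documents state no SSE rate, no death rate and no power for either endpoint.

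**Inputs**
- SSE by month 24 on the 1-KM scale, p: assumed 5% to 30%.
- Death hazard: from overall-survival medians cited in Protocol 1.1. These are 34.7 months (ADT alone, abiraterone trial), and 44.0 months (ADT alone) and 57.6 months (docetaxel plus ADT) in the docetaxel trial. The full hazard is used first, then half of it.
- Hazards constant over time.

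**Formulas**
- h1 = -ln(1 - p)/24 (SSE); h2 = ln 2 / survival median (death).
- 1-KM(t) = 1 - exp(-h1 t).
- Cumulative incidence(t) = h1/(h1 + h2) x [1 - exp(-(h1 + h2) t)].

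**Worked case: survival median 44.0 months, p = 20%, t = 24**
- h1 = 0.2231/24 = 0.00930; h2 = 0.6931/44.0 = 0.01575; sum 0.02505.
- 1-KM = 20.0%.
- Cumulative incidence = 0.371 x (1 - 0.548) = 16.8%. The gap is 3.2 points.
- The Kaplan-Meier SSE-free rate of 80.0% is therefore neither the share without an SSE (83.2%) nor the share alive without one (54.8%).
- With 60 patients all followed to month 24, the Greenwood SE is the square root of 0.64 x 0.371/60 x (1/0.548 - 1), or 5.7 points. The gap is about 0.57 SE.

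**Range over all assumptions (points by which 1-KM exceeds cumulative incidence)**

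| Month | Full death hazard | Mid case (44.0 months, p = 15%) | Half the death hazard |
|---|---|---|---|
| 12 | 0.2-1.8 | 0.7 | 0.1-0.9 |
| 18 | 0.4-3.6 | 1.5 | 0.2-1.9 |
| 24 | 0.7-5.8 | 2.4 | 0.3-3.1 |

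**Difference between arms (illustration only).** Take the worked case for placebo and assume hazard ratios of 0.6 for SSE and 0.65 for death. At month 24 the overstatement is 3.2 points on placebo and 1.4 on enzalutamide. The arm difference is 7.5 points by Kaplan-Meier and 5.6 by cumulative incidence. Open-label censoring is ignored here.

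**Which time points would be tabulated.** The Synopsis assumes 15 months of recruitment plus 12 of follow-up, so a cut at month 27.
- With uniform accrual and no dropout, (27 - 24)/15 = 20% of patients can reach month 24. In the worked case, placebo at risk = 60 x 0.20 x 0.548 = 6.6, below the limit of 10. At month 18 it is 60 x 0.60 x 0.637 = 22.9. The last placebo rate would be month 18.
- With a cut about 39 months after first enrolment (assumed), all 60 could reach month 24, and 60 x 0.548 = 33 would be at risk. If placebo patients also left for open-label treatment at the 14.8-month radiographic progression median of the cited abiraterone trial's control arm, about 33 x 0.325 = 11 would remain.

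**The case against.** **The size is not known.** A reader might infer that SSE incidence will be overstated by several points. The documents do not support that as a fact. They contain no SSE or death rate for this trial. A gap of three points or more needs the higher end of the assumed rates, and mostly month 24 or later. Using the full survival hazard from randomization is also generous: entry requires ECOG 0-1 and a life expectancy of at least 12 months, so early deaths should be fewer than a constant hazard implies. This stands.

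**The placebo arm is partly shielded.** Before study-wide unblinding, only placebo patients can enter the open-label phase, after confirmed radiographic progression. They are censored at entry for both endpoints, so their later deaths never count, and fewer placebo patients stay at risk at late time points. This stands. It should make the placebo gap smaller than computed, and it is another reason why the arms may differ.

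**The comparison is unaffected.** A reader might infer that the treatment comparison is invalid. It is not: with death censored, the log-rank test and Cox model compare cause-specific hazards, and their p-values are descriptive in any case. This stands, and it limits the point to absolute rates, medians and curves.

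**The SAP reports an event-free rate, not an incidence.** That is correct, and the overstatement arises only when the complement is read as incidence. But nothing in the SAP warns against that reading or supplies the estimate a reader would want.

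**Aalen-Johansen is no cure-all.** It too assumes non-informative censoring, and censoring at open-label entry follows progression. Replacing Kaplan-Meier outright would exchange one imperfect absolute rate for another and lose comparability with other trials. This argues for adding the estimate, not for replacing the planned output.

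**Conclusion.** The point holds for the absolute summaries of both endpoints. Death is censored (explicitly for SSE, by omission for new therapy), Kaplan-Meier rates are reported by arm, and no competing-risk estimate is planned. The direction needs no trial data: 1-KM overstates cumulative incidence whenever deaths precede the event. It would be a mistake to conclude that the tabulated SSE-free percentages are too high; relative to 1 minus cumulative incidence they are too low.

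The size for SSE is conditional on the assumed rates above: from a fraction of a point to under 2 points at month 12, and at most about 6 at month 24. It is roughly halved if only half the death hazard applies before an SSE, and should be smaller on placebo because of open-label censoring. On the planned 27-month timeline, placebo rates would probably stop at month 18. A later cut is plausible, given a planned start in 3Q2019 and a SAP dated December 2022, but the documents do not fix one. No size was computed for time to new therapy. This is a worthwhile improvement to descriptive secondary results; the primary analysis, alpha and sample size are untouched.

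**What to change.** - In SAP 7.4.2.2 and 7.4.2.5, add Aalen-Johansen cumulative incidence by arm at the planned time points, with death before the event as a competing event at the death date.
- Keep the Kaplan-Meier output, the stratified log-rank test and the Cox model. Label the hazard ratio cause-specific, and state that 1-KM is not to be presented as incidence.
- In SAP 6.1.2.5, name death and treat it as in 6.1.2.2.
- State that censoring at open-label entry may be informative and limits both estimates.

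The cost is a few lines of SAP text and one extra table and figure per endpoint, from a standard procedure. Survival status is already followed, and SAP 7.12.1 already has a rule for partial death dates, so no new data are needed.
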